4.4. Treatment Assignment and Blinding

This is an open-label study in which all participants will receive a continuous, 6-hour IV infusion of brexanolone administered at the Clinic Treatment Visit on Day 1.

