7.2. Key Definitions

7.2.1. Baseline

For in-clinic assessments, baseline is defined as the most recent value immediately prior to the start of IP infusion. For remote daily assessments, baseline is defined as the average of all available preinfusion values per participant. Change from Baseline is defined as the measurement at each timepoint minus the Baseline value.

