For the treatment period (Day 1), baseline is defined as the most recent value immediately prior to the start of IP infusion, or predose. For the postinfusion remote assessment period (Days 2 through 7), baseline is defined as the average of all available preinfusion values per participant collected from Day -7 through Day -1. This will be calculated by summing the daily arithmetic means and dividing by the total number of non-missing days. If a participant is missing either a morning or evening score, then the single available score will be used as the mean for that day Missing day or partial missing day VAS ratings will not be imputed.

Descriptive statistics of both VAS component scores and VAS component change from baseline scores will be tabulated. Considering the small sample size, unbiased Hedge's g will be used to compare the effect size of the post baseline score at each timepoint to the baseline score. Hedge's g will be calculated for pre-post scores in one group using the following formula:

$$g = d \times J$$
 Where $d = \frac{(post-baseline\ mean)-(baseline\ mean)}{SD_{within}}$ and $J = 1 - \frac{3}{4(2n-2)-1}$

SD_{within} can be computed from the standard deviation of the change from baseline (SD_{CFB}) as

$$SD_{within} = SD_{CFB}/\sqrt{2(1-r)},$$

r is the correlation between baseline and post-baseline, n is the number of pairs.

The 95% CI of Hedge's g will be calculated as

$$g \pm t(n-1, 0.025) \times SE(g);$$

Where
$$SE(g) = \sqrt{Var(g)} = \sqrt{Var(d)} \times J^2 = \sqrt{\left(\frac{1}{n} + \frac{d^2}{2n}\right)2(1-r)} \left(1 - \frac{3}{4(2n-2)-1}\right)^2$$

(Borenstein et al 2009).

[figure not shown]
Each VAS component score will be analyzed separately; this will also be done separately for Day 1 (during treatment) and Days 2 to 7 (after treatment).

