For each component, a mixed-effects model for repeated measures will be considered. Each repeated measures model will include (a) change from baseline scores as the dependent variable and (b) both baseline VAS component value and visit as fixed effect independent variables. The residual errors from the same participant across visits will be modeled using an unstructured covariance matrix (UN). If the model using an unstructured covariance matrix does not converge, compound symmetry (CS) and first order autoregressive (AR(1)) covariance structures may be used, in that order. Model-based point estimates (i.e., least squares means, their 95% confidence intervals (CIs), and standard errors (SEs) will be reported. For Day 1 the repeated timepoint will be hours and for Days 2 through 7 the repeated timepoint will be days.

Example SAS code:

Line plots of least squares (LS) mean will be plotted with standard error bars. Q-Q plot for residuals will also be provided to assess normality assumptions.

Listings of observed raw scores and change from baseline values will be presented separately for each VAS component by participant.

_	

	_
	_
	4
	-
	_
	ı
	i
	
	_
	_
	-
	-

10. Safety

The Safety Set (SS) will be used for all safety analyses. Safety and tolerability of brexanolone will be evaluated by incidence of treatment-emergent adverse events

Listings for discharge and safety phone call will also be included.

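### In this single-arm model the baseline-adjusted LS-mean CIs are conditional on the observed baselines, and are too narrow for the population mean VAS change whenever change depends on baseline

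*SAP*

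**What the plan says.** There is no comparator. SAP 4.4 states: "This is an open-label study in which all participants will receive a continuous, 6-hour IV infusion of brexanolone".

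SAP 9.1 fits a repeated-measures model to each VAS component, separately for Day 1 and for Days 2 to 7. The outcome is change from baseline, the fixed effects are "both baseline VAS component value and visit as fixed effect independent variables", and the residual covariance is unstructured, with compound symmetry and then AR(1) as fallbacks. From this model, "least squares means, their 95% confidence intervals (CIs), and standard errors (SEs) will be reported". LS means are also plotted with standard error bars. Protocol 13.5 has the same fixed effects and also lists p-values, which the SAP list omits.

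SAP 7.2.1 fixes the sign: "Change from Baseline is defined as the measurement at each timepoint minus the Baseline value". The baseline differs between the two models. For Day 1: "For the treatment period (Day 1), baseline is defined as the most recent value immediately prior to the start of IP infusion, or predose". For Days 2 to 7, "baseline is defined as the average of all available preinfusion values per participant collected from Day -7 through Day -1".

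The VAS endpoints in SAP 5.2 are secondary and are worded as plain changes from baseline. SAP 7.1 and 9.1 also tabulate change with n, mean and SD at each time point, and SAP 9.1 adds Hedges' g with a 95% CI. The visible text does not give the baseline value at which LS means are evaluated or the degrees-of-freedom method, and it does not say that the LS-mean CIs are conditional on the observed baselines.

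**The concern.** Baseline adjustment earns its place in a comparison of arms, where it removes chance imbalance and noise from the treatment contrast. Here the target is a single mean change. Had other participants been enrolled, their average baseline would have differed, and so would their average change if change is related to baseline. The adjusted model treats the sample's mean baseline as fixed and leaves that source of variation out of the SE.

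At stake is how precisely the VAS change appears to be known in about 10 people. The shortfall is largest when louder or more annoying tinnitus falls by more points, because the post-dose spread then shrinks. If every rating fell by 30%, for example, the post-dose SD would be 0.7 of baseline. The intervals could therefore be most optimistic when the drug appears to work.

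**Working it through.** **Inputs from the documents.** One arm (SAP 4.4). Fixed effects are baseline and visit (SAP 9.1, Protocol 13.5). There are seven ratings on Day 1, at hours 0.5 to 6, and six days in the follow-up model. SAP 4.3 gives up to 24 dosed for about 20 completers (20 × 1.2 = 24; 24 × 0.8 = 19.2). SAP 12 reduces this to about 10 dosed. The documents give no VAS SD, correlation, SE or CI width, so there is no stated precision to reproduce.

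**Assumptions.** LS means at the average baseline; t with n−2 df for the adjusted interval and n−1 df for the unadjusted one; normal data. Let σ be the baseline SD, k the ratio of post-dose to baseline SD, and r the correlation of baseline with the post-dose value.

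**Step 1: the estimate.** The centred baseline sums to zero over participants, so with complete data it is orthogonal to the visit terms. The LS mean at the average baseline then equals the raw mean change at that visit.

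**Step 2: the standard error.**
- Variance of change: σ²(1 + k² − 2rk)
- Slope of change on baseline: rk − 1
- Residual variance: k²σ²(1 − r²)
- Model SE² = residual variance / n
- SE² for the population mean change = (residual variance + slope² × σ²) / n

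The SE ratio is √[k²(1 − r²) / (1 + k² − 2rk)], which is √[(1 + r)/2] when k = 1.

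**Step 3: one-visit model, n = 10 (σ = 1).** Coverage is from simulation, nominal 95%.

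| k | r | Var(change) | Residual var | SE ratio | Adjusted CI coverage |
|---|---|---|---|---|---|
| 1.0 | 0.3 | 1.40 | 0.91 | 0.81 | about 90% |
| 1.0 | 0.5 | 1.00 | 0.75 | 0.87 | about 92% |
| 1.0 | 0.7 | 0.60 | 0.51 | 0.92 | about 93% |
| 0.7 | 0.3 | 1.07 | 0.446 | 0.65 | about 83% |
| 0.7 | 0.5 | 0.79 | 0.368 | 0.68 | about 85% |
| 0.7 | 0.7 | 0.51 | 0.25 | 0.70 | about 86% |
| 1.4 | 0.3 | 2.12 | 1.784 | 0.92 | about 93% |
| 1.4 | 0.7 | 1.00 | 1.00 | 1.00 | about 95% |

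At k = 1.2, coverage is about 92, 94 and 95% for r = 0.3, 0.5 and 0.7. The one-sample t interval covers 95% throughout. With a zero slope the adjusted interval also covers 95%.

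**Step 4: the planned model.** Seven time points, unstructured REML, complete data, between-visit correlation assumed to be 0.8:
- n = 10, equal SDs: about 92 to 95% for r = 0.3 to 0.7
- n = 10, k = 0.7: about 85 to 88%
- n = 20, equal SDs: about 89 to 93%
- n = 20, k = 0.7: roughly 80 to 85%

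At n = 10 the noise in estimating the covariance matrix inflates the SE and partly offsets the narrowing. With equal SDs and r of 0.7 or more it offsets most of it. At n = 20 that offset is largely gone, so more participants do not cure the problem.

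**Step 5: dropout.** With 20% dropout completely at random over six visits (n = 10, r = 0.5, equal SDs, SD units), the true sampling SD is 0.331 unadjusted and 0.332 adjusted. The model SEs are 0.334 and 0.294. Adjustment gains nothing, and its SE is about 11% low (0.294/0.332 = 0.89).

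**Step 6: in VAS points.** Assume baseline SD 20, n = 10, r = 0.5, one visit.
- Post-dose SD 20: unadjusted SE √(400/10) = 6.32, half-width 2.262 × 6.32 = 14.3. Adjusted SE √(300/10) = 5.48, half-width 2.306 × 5.48 = 12.6.
- Post-dose SD 14: change variance 400 + 196 − 280 = 316, SE 5.62, half-width 12.7. Residual variance 196 × 0.75 = 147, SE 3.83, half-width 8.8.

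**The case against.** The strongest reply is about the target. Nothing in the documents defines the estimand as a mean change over a wider population of baselines, and about 10 people at one or two sites are not a random sample. Given the observed baselines, the planned CI has its nominal coverage. This is correct as far as it goes. But the endpoint is worded as a plain change from baseline, and nothing visible tells the reader that the interval is conditional, so most will take it as the precision of the mean change.

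Second, unadjusted information is already planned, in the descriptive tables and in Hedges' g, whose CI uses the SD of change with n−1 df. This stands, and it limits the harm. But Hedges' g is standardised and is not an interval in VAS points, and the descriptive tables carry no CI.

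Third, the size is uncertain. Responses that differ widely between people can raise the post-dose SD, and coverage is then 92 to 95% in the one-visit case. The Days 2 to 7 baseline averages up to 14 ratings, so its correlation with later values is probably higher and the loss smaller than on Day 1. The CS and AR(1) fallbacks were not examined. All of this stands.

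Fourth, if dropout depends on baseline, the adjusted model may reduce bias, and Protocol 13.5 prespecifies it. This is a reason to keep it, not to replace it.

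A reader might infer that the LS-mean CIs are simply invalid, that true coverage in this trial is 83 to 86%, or that the study's main efficacy result is unsound. The documents support none of these. The intervals are valid conditionally. The low figures come from one assumed SD ratio in a one-visit model. The SAP gives the LS means no priority over the descriptive results, and the primary endpoint is TEAE incidence.

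**Conclusion.** The point holds as a moderate reporting issue. In a single arm, with LS means at the average baseline, adjustment leaves the complete-data estimate unchanged, while its SE omits slope² × baseline variance. The CI is too narrow for the population mean change unless the slope is near zero. In the planned model at n of about 10, the loss ranges from almost nothing to about 10 percentage points of coverage over the cases examined (r from 0.3 to 0.7, SD ratio 1.0 or 0.7). Where this trial falls cannot be told from the documents.

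The conclusion depends on the reference baseline and df method, neither of which is visible. No test or decision rule in the SAP is tied to these intervals, so the consequence is overstated precision in description and not a wrong trial decision.

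**What to change.** In SAP 9.1:
- At each time point, report the mean change with a 95% CI from the repeated-measures model with visit as the only fixed effect, or a one-sample t interval from the n, mean and SD already tabulated. Use this interval for statements about the size of the VAS change.
- Keep the protocol's baseline-adjusted model alongside it. State the baseline value at which LS means are evaluated and the df method, and label its CIs and SE bars as conditional on the observed baselines.
- Record the addition in SAP Section 12.

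The cost is one extra model or table column and a few lines of text; no new data are needed. The reported intervals will usually be wider, from almost no change to about 50% (in the one-visit case at n = 10, SD ratio 0.7 and r = 0.3, the adjusted width is 0.66 of the unadjusted, and 1/0.66 = 1.52). The one-sample t interval uses only participants observed at that time point, so the visit-only model is the better choice if ratings are missing.

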6. STUDY OBJECTIVES AND ENDPOINTS

Objectives	Endpoints
Primary	
To evaluate the safety and tolerability of brexanolone	Incidence of treatment-emergent adverse events (TEAEs)
Secondary	
To assess subjective tinnitus perception during brexanolone infusion based on Visual Analog Scales (VAS)	 Change from baseline to Hour 6 of infusion in VAS loudness (VAS-L) ratings Change from baseline to Hour 6 of infusion in VAS annoyance (VAS-A) ratings
To assess subjective tinnitus perception after brexanolone infusion based on VAS	 Change from baseline to post-infusion in VAS-L ratings measured via daily diary over multiple days
	 Change from baseline to post-infusion in VAS-A ratings measured via daily diary over multiple days
1	I  
_	
	Change from baseline in vital signs, electrocardiogram (ECG), and clinical laboratory parameters

[figure not shown]

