13.5. Efficacy Analysis

Efficacy analyses will primarily be based on the Efficacy Set.

The two secondary endpoints of this study are (a) tinnitus perception during brexanolone infusion based on the VAS and (b) tinnitus perception after brexanolone infusion based on VAS. For remote assessments, ratings for both VAS-L and VAS-A will be obtained twice daily, once each in the morning and evening, during the both the Screening Period and on Day 2 to Day 7.

The daily arithmetic means of remote VAS-A and VAS-L ratings obtained during the Screening Period will be computed and used descriptively. The daily arithmetic means of remote VAS-A and VAS-L ratings obtained on Days 2-7 will be used both descriptively and in statistical modeling.

Each component of VAS for tinnitus will have change from baseline score (see Section 13.3 for a description of appropriate baseline for a given schedule of assessment timepoint) at each postbaseline assessment (whether during brexanolone infusion or post-brexanolone infusion) computed. Descriptive statistics of both VAS component scores and VAS component change from baseline scores will be summarized.

Each VAS component score will be analyzed separately for each secondary endpoint. This will be done separately for Day 1 (ie, during treatment) and Days 2 to 7 (ie, after treatment). The during-infusion Day 1 VAS component data will consist of VAS components obtained at 0.5, 1, 2, 3, 4, 5, and 6 hours. The post-infusion Days 2 to 7 VAS component data will consist of daily arithmetic component means.

Each analysis will utilize a mixed effects model for repeated measures. Each repeated measures model will include (a) the change from baseline score of the appropriate VAS component as the dependent variable and (b) both baseline VAS component value and visit as fixed effect independent variables. Participants will be treated as random effects.

Model- based point estimates (ie, least squares means, their 95% confidence intervals, and associated p-values) at each time point (visit) will be reported where applicable. Line plots of change from baseline scores will be plotted with standard error bars. Additional analyses will be detailed in the SAP.

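### No visible text in the protocol or SAP specifies a summary over the post-infusion days, so the post-infusion VAS endpoint has separate day-level estimates but no single pre-specified answer

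*SAP*

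**What the plan says.** Protocol Section 6 gives the objective as "To assess subjective tinnitus perception after brexanolone infusion based on VAS". The two endpoints under it are "Change from baseline to post-infusion in VAS-L ratings measured via daily diary over multiple days" and "Change from baseline to post-infusion in VAS-A ratings measured via daily diary over multiple days". SAP 5.2 carries the same two endpoints. The companion endpoints for the infusion period name their target time, Hour 6, although VAS is rated at seven times during the infusion.

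The analysis text works by day:

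- Protocol 13.5 on the data: "The post-infusion Days 2 to 7 VAS component data will consist of daily arithmetic component means". Visit is a fixed effect, and least squares means with 95% confidence intervals and p-values "at each time point (visit) will be reported where applicable".
- SAP 9.1 on the model: "For Day 1 the repeated timepoint will be hours and for Days 2 through 7 the repeated timepoint will be days". On output: "Model-based point estimates (i.e., least squares means, their 95% confidence intervals (CIs), and standard errors (SEs) will be reported". This sentence lists no p-values and does not say whether the least squares means are daily, overall or both.
- SAP 9.1 on effect size: Hedges' g is used to "compare the effect size of the post baseline score at each timepoint to the baseline score".

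SAP 9.1 averages the baseline for these endpoints over Day -7 to Day -1. Protocol 13.5.1 applies no multiplicity adjustment. SAP Section 12 expects about 10 participants to be dosed instead of 24.

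**The concern.** The endpoint runs from baseline to a post-infusion period, but the visible analysis text does not say how that period becomes one number. The baseline side pools up to 14 ratings (two a day for seven days). The post-infusion side stays as single days with at most two ratings each, and the schedule footnotes give Day 7 a morning rating only. The infusion endpoint shows that the authors could name a target when they wanted one.

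The stake is the clarity of the answer. A reader who asks whether tinnitus perception changed after the infusion gets six least squares means per scale, and six values of Hedges' g per scale. With about 10 people the daily intervals will be wide and may not agree with each other. Nothing fixes in advance which figure stands for the endpoint, so the choice could be made after the results are seen.

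**Working it through.** **The plan's own figure.** The only sample-size figure is up to 24 dosed for about 20 completers at 20% discontinuation. 24 × 0.8 = 19.2, and 20 × 1.2 = 24, so it reproduces to rounding (20/0.8 would give 25). The documents state no SD, between-day correlation or target precision for the VAS endpoints. The between-day correlation ρ below is therefore an assumption, shown over a range.

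**Count of estimates.** Days 2 to 7 are 6 days; 6 days × 2 scales = 12 least squares means.

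**Standard error of the average against one day.** Assume equal variance on each day, complete data, and correlation ρ between any two days of the baseline-adjusted change (compound symmetry, the SAP's first fallback structure). For the equal-weight average of six days:

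SE ratio = √((1 + 5ρ)/6)

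| ρ (assumed) | Ratio | Reduction |
|---|---|---|
| 0.4 | √(3.0/6) = 0.707 | 29% |
| 0.6 | √(4.0/6) = 0.816 | 18% |
| 0.8 | √(5.0/6) = 0.913 | 9% |
| 0.9 | √(5.5/6) = 0.957 | 4% |

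Under AR(1), the second fallback, the ratio is the square root of (1/36)[6 + 2(5ρ + 4ρ² + 3ρ³ + 2ρ⁴ + ρ⁵)]. It is 0.684, 0.825 and 0.908 at ρ = 0.6, 0.8 and 0.9, which is a reduction of 32%, 18% and 9%.

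**Leaving Day 7 out.** For Days 2 to 6 the ratio is √((1 + 4ρ)/5). This is √0.52 = 0.721, √0.68 = 0.825, √0.84 = 0.917 and √0.92 = 0.959 at ρ = 0.4, 0.6, 0.8 and 0.9, or 28%, 18%, 8% and 4%. Precision hardly depends on whether Day 7 is included.

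**Interval width at n = 10.** In units of the SD of one day's change, the half-width for one day is t(0.975, 8)/√10 = 2.306/3.162 = 0.73. For the six-day average under compound symmetry it is 0.60, 0.67 and 0.70 at ρ = 0.6, 0.8 and 0.9.

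**How often the days give mixed messages.** A simulation used n = 10, 40,000 trials, a one-sample t interval for each day and compound symmetry. It is simpler than the planned model.

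- With no true change, at least one of six 95% intervals excludes zero in 22%, 15% and 12% of trials at ρ = 0.5, 0.8 and 0.9. The average does so in 5%.
- With an assumed constant change of 0.6 SD, some but not all of the six intervals exclude zero in 73%, 47% and 34% of trials. The average excludes zero in 60%, 46% and 42%; any one day does so in about 40%.

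**The case against.** Four points count on the other side.

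**The endpoint wording is open.** The phrase about multiple days can describe how the ratings are collected instead of a single averaged quantity. Protocol 13.5 computes change at each assessment and models daily means. On that reading endpoint and analysis agree. This stands: a reader might infer a contradiction between the two, but the documents show only that no summary is specified.

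**An overall estimate may exist.** The SAP's example SAS code is not visible, and the table shells are in separate documents. Either could contain an averaged estimate. This also stands, so the claim is confined to visible text. The surrounding prose calls for no such estimate, and one sentence would settle the matter.

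**Precision is not lost in a strict sense.** The least squares mean for Day 2 answers a question about Day 2. It shares a target with the six-day average only if the effect is roughly constant, and after a single 6-hour infusion it may well wane. A daily profile is a proper way to study persistence. A reader might infer that the day-level analysis is defective; it is not. What stands is that the average is the more precise summary when the effect is stable, by an amount that could be as small as 4%.

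**Little turns on it formally.** The primary endpoint is the incidence of adverse events. These are secondary results in a single-arm, open-label study with no power calculation or decision rule. All time points are tabulated and least squares means are plotted, so selective quotation would be visible. This limits the weight of the point. It does not supply the missing pre-specified answer.

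**Conclusion.** The point holds in a limited form. The visible text of both documents gives a separate estimate for each of Days 2 to 7 on each scale. It names no average, main day or combining rule, although the infusion endpoint has its named hour. The absence of one stated answer does not depend on any assumed correlation. The precision gain does: it is 29% to 4% of the standard error for ρ from 0.4 to 0.9, and it requires a roughly constant effect, equal daily variances and compound symmetry.

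A reader might take the simulated 12% to 22% as an inflated type I error rate. The documents do not support that, because no formal test or error rate is claimed for these endpoints. The figures show only how easily one of several intervals can stand out by chance. This is a low-cost improvement to a descriptive secondary analysis.

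**What to change.** Before database lock, add to SAP 9.1 one contrast per scale from the planned Days 2 to 7 model: the equal-weight average of the daily least squares means, with its 95% confidence interval. Name it as the summary for the post-infusion endpoint, and keep the daily least squares means as the time course.

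State the days and weights, because Day 7 is not like the others. It has a morning diary rating only, the end-of-study visit may fall a day either side, and SAP 7.4 applies no visit windows. Two choices are workable:

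- Days 2 to 6, weight 1/5 each: the days with two scheduled diary ratings.
- Days 2 to 7, weight 1/6 each, with a statement that Day 7 is morning-only.

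If the example code or the table shells already contain such an estimate, say so in the text and give its weights.

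The cost is a sentence or two in the SAP, one ESTIMATE or LSMESTIMATE statement and one extra table row per scale. No new data or model is needed, and the contrast works under the unstructured matrix or either fallback. The downside is dilution: a change of size D on one day only appears as D/5 or D/6 in the average. The daily estimates still show it.
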